7.1 Sample size and power considerations

Previous data showed that VT/VF episodes are decrease by two thirds within 6 months after initiation of sacubitril/valsartan in ICD±CRT patients (10). sVT/VF Episodes declined by 62.5% whereas nsVTs rate dropped by ~70%. Based on comparable effects on heart failure morbidity with either SGLT-2 inhibition or sacubitril/valsartan treatment we expect a profound reduction in sVT/VF in the treatment arm. Since data of the large SGLT2 outcome trials which did not focus on arrhythmias and their detection but only counted cases of sudden cardiac death have a signal of smaller effects we calculate with a decrease in the event rate of 30%. Moreover, the retrospective analysis by Martens et al provides a rather low event rate in their population. However, as pointed out in the Introduction other prospective randomized trials have considerably higher event rates. The sample size calculation is based on the mathematical formula provided by Zhu and Lakkis for comparing event rates of two negative binomial distributions (19). We used the function power.nb.test of the package MKmisc in R that implements the results of the paper cited above. According to that formula, the parameters needed to calculate the sample size are: The expected yearly rate of VT/VF episodes in the control group (r_0), The minimal clinical relevant effect (RR) defined here as the ratio of expected VT/VF episodes rates (RR = expected rate in treated/expected rate in control = r_1/r_0), the average follow-up or treatment duration (duration), the negative binomial dispersion parameter (k), the Type I error probability (α) and the power ($1 - \beta$). To detect a 30% reduction in VT/VF episodes rate in the ertugliflozin group as compared to the placebo group (i.e. using RR = 0.70), with a power of 80% and an alpha-level of 0.05%, a sample size of 191 patients in each group is needed. In this sample size calculation, we assumed the dispersion parameter k to be 1.0, the expected yearly rate of VT/VF episodes in the control group (i.e. r_0) to be 1.0 and an average follow-up of 11.4 months. To account for a dropout rate of about 5% in each group, we will need of 402 patients in each arm.

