7.2 Data analysis

Intention-to-treat (ITT) analyses will be applied as the primary analysis. Analysis of the primary endpoint is comparison of the number of sVT/VF episodes between treatment groups from randomization to week 52. The primary endpoint will be analysed using analysis of covariance (ANCOVA), with treatment as a fixed factor, the baseline number of sVT/VF episodes as a covariate and with adjustment for history of T2D and eGFR and site of randomization.

Normally distributed variables will be presented as mean \pm standard deviation (SD) and skewed distributed variables as median and interquartile range [IQR]. Comparisons between treatment and placebo group will be performed by an unpaired two sample *t*-test, Mann–Whitney test, or χ^2 test as appropriate.

A two-tailed p-value ≤ 0.05 will be considered statistically significant. A detailed statistical analysis plan including pre-specified subgroup analyses will be finalized ahead of database lock.

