### **3 Study Methods**

#### **3.1 General Study Design and Plan**

This is a two arms randomized controlled multi-center, parallel-group, double-blinded trial. The control group is a placebo and the treated group is Ertugliflozin. The aim of the trial is to show superiority of Ertugliflozin over Placebo in HFrEF and HFmrEF patients with ICD±CRT therapy.

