## Ertugliflozin to Reduce Arrhythmic burden in ICD/CRT patientS (ERASE-Trial) – a phase III Study

on the mathematical formula provided by Zhu and Lakkis for comparing event rates of two negative binomial distributions (11). We used the function `power.nb.test` of the package `MKmisc` in R that implements the results of the paper cited above. According to that formula, the parameters needed to calculate the sample size are: The expected yearly rate of VT/VF episodes in the control group ( $r_0$ ), The minimal clinical relevant effect (RR) defined here as the ratio of expected VT/VF episodes rates (RR = expected rate in treated/expected rate in control =  $r_1/r_0$ ), the average follow-up or treatment duration (duration), the negative binomial dispersion parameter ( $k$ ), the Type I error probability ( $\alpha$ ) and the power ( $1 - \beta$ ). To detect a 30% reduction in VT/VF episodes rate in the ertugliflozin group as compared to the placebo group (i.e. using RR = 0.70), with a power of 80% and an alpha-level of 0.05%, a sample size of 191 patients in each group is needed. In this sample size calculation, we assumed the dispersion parameter  $k$  to be 1.0, the expected yearly rate of VT/VF episodes in the control group (i.e.  $r_0$ ) to be 1.3 and an average follow-up of 11.4 months. To account for a dropout rate of about 5% in each group, we will need of 402 patients in total.

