**Ertugliflozin to Reduce Arrhythmic burden in ICD/CRT patientS (ERASE-Trial) – a phase III Study**

## 7 Summary of Changes to the SAP

This is the revised version of the SAP. It was revised due to the early termination of the trial and the corresponding lower sample size.

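### The SAP was revised because the trial stopped early with fewer patients, but its sample-size section still gives 402 patients and 80% power, unmarked as the superseded plan

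*SAP*

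**What the plan says.** SAP section 7 gives one reason for the revision: "It was revised due to the early termination of the trial and the corresponding lower sample size".

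SAP section 4, in that same version, sets out the design calculation in the present and future tense. The target is "To detect a 30% reduction in VT/VF episodes rate in the ertugliflozin group as compared to the placebo group", "with a power of 80% and an alpha-level of 0.05%, a sample size of 191 patients in each group is needed". The control rate is assumed "to be 1.3 and an average follow-up of 11.4 months", with dispersion 1.0. It ends: "To account for a dropout rate of about 5% in each group, we will need of 402 patients in total". Nothing in the section says that these figures belong to a plan that was not carried through.

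Neither document gives the number randomised, the patient-years accrued, or the power or precision to be expected at the reduced size. The effect of the smaller sample shows only indirectly. SAP 5.1 makes adjustment for the stratification factors, and SAP 5.2 makes imputation for the primary analysis, depend on whether the sample is large enough. Neither gives a threshold.

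**The concern.** Section 7 describes the state of the trial that this version governs, and section 4 is current text in the same version. The two do not agree on how large the trial is. The reason for the revision did not reach the section that it most directly affects.

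What is at stake is how the primary result is read. SAP section 5 sets a single test of no treatment effect and does not say how a non-significant result will be interpreted. With 80% power for a 30% reduction on record, a reader could take p > 0.05 as evidence against a reduction of that size. A smaller trial gives less support for that inference than the stated power suggests, and the SAP does not say how much less.

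**Working it through.** **Inputs**
- Rate ratio RR = 0.70, dispersion k = 1.0, control rate r0 = 1.3 per year, follow-up t = 11.4/12 = 0.95 year, equal groups, 5% dropout: SAP section 4. Treated rate r1 = 0.70 × 1.3 = 0.91.
- Alpha: printed as 0.05% in SAP section 4, taken here as 0.05.
- Sidedness: two-sided. Protocol 7.2 says "A two-tailed p-value ≤ 0.05 will be considered statistically significant", and the alternative hypothesis in SAP section 5 is also two-sided.
- Number randomised: not given. Sizes below 191 per arm are assumptions.

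**Step 1: reproduce the plan's figure**

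Zhu–Lakkis formula, n per arm = [z_α √V0 + z_β √V1]² / (ln RR)².
- V1 = (1/t)(1/r0 + 1/r1) + 2k = (1/0.95)(0.7692 + 1.0989) + 2 = 3.966
- V0 (maximum-likelihood version, common rate (1.3 + 0.91)/2 = 1.105) = 2/(0.95 × 1.105) + 2 = 3.905
- (ln 0.70)² = 0.1272

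One-sided 5%: (1.645 × 1.976 + 0.842 × 1.992)² / 0.1272 = 190.8, so 191. Total: 2 × 191/0.95 = 402.1. Both plan figures reproduce.

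Two-sided 5%: (1.960 × 1.976 + 0.842 × 1.992)² / 0.1272 = 242.1, so 243 per arm. The three variance versions of the formula give 230 to 245.

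So 402 patients give 80% power only with a one-sided 5% test. With the two-sided test that the documents specify, 191 per arm gives about 70%. That is the baseline against which the effect of early stopping should be measured.

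**Step 2: power and precision at smaller sizes**

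Two-sided 5%, using V = V1 = 3.966 throughout:
- SE(ln RR) = √(3.966/n)
- Power = Φ(0.3567/SE − 1.96)
- 95% CI for an observed RR of 0.70 = 0.70 × exp(±1.96 SE)

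| Analysed per arm | SE | Power for RR 0.70 | 95% CI if observed RR is 0.70 |
|---|---|---|---|
| 191 (planned) | 0.144 | 70% | 0.53 to 0.93 |
| 150 (assumed) | 0.163 | 59% | 0.51 to 0.96 |
| 100 (assumed) | 0.199 | 43% | 0.47 to 1.03 |
| 50 (assumed) | 0.282 | 24% | 0.40 to 1.22 |

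**Step 3: sensitivity to the control rate**

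Protocol 7.1 uses a different rate, "to be 1.0 and an average follow-up of 11.4 months". Then V = (1/0.95)(1 + 1/0.70) + 2 = 4.556, and power is 64% at 191, 53% at 150, 39% at 100 and 22% at 50 per arm. This rate does not reproduce 191 (219 one-sided, 278 two-sided), so the main table uses the SAP's 1.3.

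**Step 4: what the table holds fixed**

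Follow-up stays at 0.95 year. The documents do not say whether early termination also shortened follow-up. If it did, t falls, V rises and power is lower at each n. Patient-years are therefore needed as well as the number randomised.

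**The case against.** The best case for the SAP is that section 4 records how the trial was designed. Keeping that record in a revised SAP is legitimate, and it contains no arithmetic slip on this point. That stands: the defect is an inconsistency and a missing label. A reader who reaches section 7 is told that the planned size was not met, and SAP 6.1 plans a flow diagram with spaces for the numbers randomised and allocated, so the achieved size will be reported with the results. That too is fair. It does not tell readers of the plan which power figure applies, and it does not settle in advance how a non-significant result is to be read.

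Three stronger readings are tempting, and the documents do not support them.
- **The trial has very low power.** This needs a small n, and none is given. A stop close to target would cost little.
- **The confidence interval will probably include no effect.** This depends on the unknown n. At 150 per arm an observed rate ratio of 0.70 has an interval of about 0.51 to 0.96 (0.50 to 0.99 at a control rate of 1.0), which excludes 1.
- **The whole shortfall from 80% comes from stopping early.** On a two-sided test the planned size already gives about 70%, so the first 10 points have another cause.

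Nor does the stated aim in SAP 3.1, "The aim of the trial is to show superiority of Ertugliflozin over Placebo", conflict with early termination. It gives the direction of the hypothesis and makes no claim about size.

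Finally, nothing in the documents requires a rule for interpreting non-significance. Adding one is good practice and does not correct a contradiction.

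**Conclusion.** The point holds as an inconsistency within the SAP. Section 7 says that the sample is smaller than planned, and section 4 presents the planned size and its power as current. Under the stated assumptions, 402 is the size that gives 80% on the one-sided basis and about 70% on the two-sided basis, so any smaller trial has less than the stated power on either reading.

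How much less cannot be determined from the documents. For illustration, the two-sided figure falls from about 70% at 191 per arm to 59%, 43% and 24% at assumed sizes of 150, 100 and 50. These figures rest on a rate ratio of 0.70, dispersion 1, a control rate of 1.3 per year and full 0.95-year follow-up. Only the fall from 70% is attributable to early stopping.

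This should be corrected before the results are interpreted. It changes no estimate, test or dataset.

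**What to change.** 1. **SAP section 4:** label the existing calculation as the original plan, superseded by early termination. Beneath it, state the number randomised in each arm and the patient-years at termination, with the expected 95% confidence-interval width for the rate ratio at that size. Power for a rate ratio of 0.70 may be added; the interval width is the more useful figure.
2. **SAP section 5:** state that the primary result is interpreted by the rate ratio with its 95% confidence interval, and that a non-significant result whose interval still includes 0.70 will not be reported as evidence against a 30% reduction.

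The cost is SAP wording only; no data, endpoint or procedure changes. The drawback for the sponsor is that the stated power becomes less favourable.

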## 5 Statistical analysis

The Negative Binomial Regression model will be used to analyse the primary endpoint (number of sVT/VF episodes from randomization to week 52). These models are suitable when comparing recurrent event rates in different groups. They allow investigation of the treatment effect and confounding variables, and adjust for variable follow-up times by using time at risk as the offset. They are a generalization of the more commonly used Poisson regression models (in case of over-dispersion) and are also superior to different Cox-regression methods. We will model the expected number of sVT/VF episodes as follows:

$$\log(\mu_{ij}) = \log(t_{ij}) + \beta_0 + \beta_1 x_{ij}$$

Where  $t_{ij}$  is the exposure time of patient  $i$  in group  $j$  ( $j = 1$  if control;  $j=2$  if treated),  $\mu_{ij}$  is the expected number of sVT/VF episodes of patient  $i$  in group  $j$  during the exposure period  $t_{ij}$  and  $x_{ij}$  is the treatment indicator of patient  $i$  in group  $j$  ( $x_{ij} = 0$  if  $j=1$  (control) and 1 if  $j = 2$  (treated)). It can be shown from the equation above that the yearly rate ratio between treated and controls is a direct function of the parameter  $\beta_1$  and can be derived as

## **Ertugliflozin to Reduce Arrhythmic burden in ICD/CRT patientS (ERASe-Trial) – a phase III Study**

**RR =  $e^{\beta_1}$ .** The efficacy of the drug, compared to placebo, will then be investigated by testing the following null and alternative hypotheses:

$$H_0: \beta_1 = 0 \quad \text{vs.} \quad H_A: \beta_1 \neq 0$$

The function `glm.nb` from the MASS package in R will be used for this reason and for fitting the negative binomial regression model. The model will also adjust for the baseline number of sVT/VF. Sensitivity analysis will be carried out by using methods robust to outliers.

The analysis of secondary endpoints will be as follows: The number of incident nsVT, the number of appropriate ICD-treatment episodes, the total number of hospitalization due to heart failure will be analysed using a beta binomial model. The change in NTproBNP and the change in HbA1c levels from randomization to week 52 will be analysed using a multiple linear regression model. Hospitalization days from randomization to week 52 will be compared between the two groups using mean and SD. Cardiovascular mortality will be analysed by comparing proportions across the two groups.

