7. STATISTICAL ANALYSES

The sample size calculations and the primary statistical method are based on the primary endpoint, which is the number of VT/VF episodes from randomization to week 52. The primary objective is to compare the rate of VT/VF episodes across the two experimental arms. The number of VT/VF episodes within 52 weeks can be considered as a discrete variable with relatively few possible values (0, 1, 2, 3 ...) per patient. This fact prevent us from using the most common statistical methods in clinical trials that assume normality, such as Student's t-test, linear regression or

analysis of variance. We, instead, will use the negative binomial regression model, which is most appropriate in the case of recurrent events (the current situation), allows investigation of the treatment effect and confounding variables, and adjusts for variable follow-up times by using time at risk as the offset. For more details on the arguments to use the negative binomial models in this kind of research, please see: (18). Furthermore, the negative binomial will be used instead of the Poisson distribution (also used for modelling count data) due to expected over-dispersion in the data.

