##### **2.2.2 Secondary endpoints**

Secondary endpoints are as follows:

- The number of incident non-sustained ventricular tachycardia (nsVT) from randomization to week 52
- The number of appropriate ICD-treatment episodes from randomization to week 52
- The number of hospitalization due to heart failure from randomization to week 52
- The total number of hospitalization days from randomization to week 52
- The change in NTproBNP from randomization to week 52.
- The change in HbA1c levels from randomization to week 52.
- Cardiovascular mortality from randomization to week 52.

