### **5.1 Covariates and subgroups**

All analyses, including the primary analysis, will be adjusted for the variables used when stratifying the randomization if the sample size permits. Analysis may also be adjusted for baseline levels of the dependent variables if available. No subgroup analyses are planned.

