## Ertugliflozin to Reduce Arrhythmic burden in ICD/CRT patientS (ERASe-Trial) – a phase III Study

### 5.4 Multiple Testing

There is no need to control for the overall type I error using multiple testing procedure since we have one single primary efficacy endpoint. The overall type I error will also not be controlled for when analysing secondary endpoints.

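### SAP section 5 applies a beta-binomial model to three open-ended event counts without a denominator, exposure term or effect measure

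*SAP*

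**What the plan says.** The sentence at issue is in SAP section 5, in the paragraph on secondary endpoints. It covers nsVT, appropriate ICD-treatment episodes and, as its third item, "the total number of hospitalization due to heart failure will be analysed using a beta binomial model". Nothing more is said about that model.

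SAP section 2.2.2 defines the three endpoints as plain counts, for example "The number of incident non-sustained ventricular tachycardia (nsVT) from randomization to week 52". None has a denominator or a cap.

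For the primary endpoint, also a count of recurrent events, SAP section 5 specifies negative binomial regression and argues that such models "adjust for variable follow-up times by using time at risk as the offset". Protocol section 7 takes the same view of negative binomial regression, "which is most appropriate in the case of recurrent events (the current situation").

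SAP section 5.1 adds the stratification factors to every analysis and then says: "Analysis may also be adjusted for baseline levels of the dependent variables if available". That supplies covariates but no exposure term. Protocol section 7.2 names only generic two-sample tests for group comparisons, so it does not fill the gap. The term beta binomial occurs nowhere else in either document.

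**The concern.** A beta-binomial needs, for each patient, a number of trials out of which the events occur. With the usual logit link it returns an odds ratio per trial. An episode count has no such number, so the analyst would have to supply one. A common denominator must be at least as large as the largest observed count, and that is known only after the data are seen. SAP section 3.2.1 shows that eligible patients may have more than 100 nsVTs in a year, so no natural ceiling exists.

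Three things are at stake:

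- **Reproducibility.** Two competent analysts could not be expected to obtain the same result for three of the seven secondary endpoints.
- **Comparability.** An odds ratio per trial does not sit beside the rate ratio reported for the primary endpoint.
- **Bias.** With one denominator for everyone, a patient who leaves early simply has fewer events. A difference between arms in death or withdrawal would then be read as a drug effect.

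**Working it through.** **1. What is specified for each model in SAP section 5**

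| Element | Primary count (sVT/VF) | Three secondary counts |
|---|---|---|
| Model | negative binomial | beta binomial |
| Number of trials | not needed | needed, not given |
| Exposure | log time at risk as offset | not given |
| Effect measure | rate ratio exp(β1) | not given |
| R function | glm.nb | not given |

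There is no plan figure to reproduce. The rest shows how much the gap can matter.

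**2. Dependence on the denominator, by formula.** Let the control mean be μ, the common denominator m and the true ratio of means 0.70. The odds ratio per trial is

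[0.7μ/(m − 0.7μ)] / [μ/(m − μ)] = 0.7(m − μ)/(m − 0.7μ).

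- m = 2μ: 0.7 × 1/1.3 = 0.54
- m = 5μ: 0.7 × 4/4.3 = 0.65
- m = 8μ: 0.7 × 7/7.3 = 0.67
- m very large: 0.70

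In simulated data at the planning values below, the largest count was typically about 8μ and never below 4μ. The value at 2μ therefore cannot arise there, and the realistic distortion from this source is small.

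**3. Dependence on follow-up, no true effect.** The inputs from SAP section 4 are a rate of 1.3 per year, k = 1, 191 per arm, "and an average follow-up of 11.4 months" (11.4/12 = 0.95 year). These are sVT/VF values, borrowed because neither document gives rates for the three endpoints. Two assumptions are not in the documents: the other arm's mean follow-up, and drop-outs leaving at a uniform time.

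For large m the null estimate should approach the ratio of mean follow-up: 0.90/0.95 = 0.947 and 0.85/0.95 = 0.895. The simulation used gamma-Poisson counts, maximum likelihood fits, a likelihood-ratio test at 5% and 1500 trials per row. The beta-binomial denominator was 1× or 3× the largest count.

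| Mean follow-up (years) | Beta-binomial ratio | Rejects | Negative binomial ratio | Rejects |
|---|---|---|---|---|
| 0.95 vs 0.95 | 1.009 / 1.008 | 5.6% / 5.8% | 1.005 | 6.2% |
| 0.95 vs 0.90 | 0.947 / 0.950 | 6.1% / 6.4% | 1.003 | 4.9% |
| 0.95 vs 0.85 | 0.890 / 0.896 | 11.3% / 11.5% | 1.002 | 4.6% |

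The Monte Carlo error near 5% is √(0.05 × 0.95/1500) = 0.6 points. Repeats of the last row with 600 and 800 trials gave ratios of 0.88 and 0.89, with 14% and 10.5% rejection. With days at risk as each patient's denominator (1000 trials) the beta-binomial gave 1.003 and 4.5%. The fault is thus the missing exposure term, not the distribution alone.

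**4. Smaller samples.** The SAP's section 7 says of the SAP: "It was revised due to the early termination of the trial and the corresponding lower sample size". It gives no number. Assumed sizes, 0.95 vs 0.85 year, 1200 trials:

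| Per arm | Beta-binomial | Negative binomial |
|---|---|---|
| 50 | 0.882, 7.0% | 0.996, 6.3% |
| 25 | 0.873, 5.2% | 0.993, 6.1% |

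The bias stays; the excess type I error largely goes.

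**5. True ratio 0.70, equal follow-up** (250 trials; denominator 1× / 3× / 20× the largest count). With a denominator well above the mean, the beta-binomial variance is roughly linear in the mean. The negative binomial in glm.nb has quadratic variance, μ + kμ².

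| True variance | Rate 1.3 | Rate 10 (assumed) |
|---|---|---|
| Quadratic | 0.730 / 0.742 / 0.746 | 0.761 / 0.781 / 0.788 |
| Linear | 0.686 / 0.700 / 0.705 | 0.682 / 0.696 / 0.702 |

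Negative binomial gave 0.702–0.706 throughout. Within a cell the choice of denominator moves the estimate by 2–4%, for example 0.746/0.730 = 1.022 and 0.788/0.761 = 1.035.

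**The case against.** The strongest reply is that the harmful case is extreme. If drop-outs leave at a uniform time, mean follow-up in years is 1 − d/2 for a drop-out proportion d. Then 0.95 versus 0.85 means 10% versus 30% drop-out, whereas SAP section 4 plans about 5% in each arm. At 5% in both arms, two sets of runs gave beta-binomial ratios of 0.98 and 0.995 with 6% and 3.4% rejection. At 5% versus 10% the ratio was 0.97 with 5.5% rejection (negative binomial 5.8%). This stands: under the plan's own drop-out assumption there is no error inflation, and the 11% should not be read as expected.

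It is also fair that 191 per arm will not be reached, that the rate of 1.3 does not describe nsVT or heart-failure hospitalisation, and that the choice of a common denominator matters little. On multiplicity the SAP (section 5.4) says: "The overall type I error will also not be controlled for when analysing secondary endpoints". The consequence is therefore confined to supportive results.

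Finally, a beta-binomial is not impossible. Days at risk would serve as a denominator. For ICD therapy, treated episodes out of detected episodes would be a proper proportion, though that answers a different question from the endpoint in section 2.2.2.

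None of this supplies what the SAP leaves out. A reader still cannot tell which analysis will be run.

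**Conclusion.** The point holds and should be fixed. Three counts without an upper limit are assigned to a model that needs a number of trials. The plan gives no trials, exposure term or effect measure, and its own argument favours a different model for this kind of data. That the term is a slip for negative binomial is a reasonable inference, not something the documents establish.

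The numerical effect depends on how the gap is filled. With a common denominator and balanced follow-up it is negligible under the null. With mean follow-up of 0.95 versus 0.85 year, which is assumed, the ratio is biased by about 11% towards the arm with shorter follow-up, and at 191 per arm type I error roughly doubles. At 25 to 50 per arm the bias remains, with little excess error. The rates and dispersion behind these figures are borrowed from sVT/VF. The primary analysis and the sample size are not affected.

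**What to change.** Confirm which model is meant. If negative binomial, replace the sentence with:

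> Counts of incident nsVT, appropriate ICD-treatment episodes and heart-failure hospitalisations will each be modelled by negative binomial regression with log(time at risk) as offset, adjusted for the stratification factors (section 5.1) and, where available, for the baseline count, entered as in the primary model. Rate ratios with 95% confidence intervals will be reported.

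If a beta-binomial is truly intended, state each patient's denominator (days at risk, for example), the link and the effect measure. In either case, say which adjustment factors are dropped if the smaller sample cannot support them; heart-failure hospitalisations are the likeliest to be sparse. If treatment codes have already been opened, report that the model was settled afterwards.

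The cost is one sentence and code already planned for the primary endpoint. There is a trade-off in power. At rate 1.3 and a true ratio of 0.70, negative binomial had 62% against 72% for the beta-binomial when variance was linear in the mean, and 65% against 57% when it was quadratic. If these come from the 250-trial runs, each carries a Monte Carlo error of about √(0.6 × 0.4/250) = 3 points. A separate run with quadratic variance gave 70% against 60%.
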